## 9.2 Sample Size and Accrual

The results of a Phase I trial of ceritinib in *ALK*-rearranged metastatic adenocarcinoma were reported recently (Shaw et al., 2014). Ceritinib demonstrated activity in patients with an overall response rate of 57% at doses of 400 mg or greater. The PFS reported was 7 months for those with prior crizotinib treatment and 10 months for those who had not received any crizotinib. Toxicities and adverse events were also reported. This study offers contemporary, relevant historical control data for comparison purposes.

The sample size calculation is based on the primary endpoint, progression-free survival, and the assumption that patients are randomized until the end of accrual. The sample size is calculated separately for each cohort.

### *Cohort A (no prior ALK-inhibitor):*

A sample size of 18 patients achieves 80% power to detect the difference between the null hypothesis of median PFS of 10 months and the alternative hypothesis of median PFS of 20 months at two-sided significance level of 0.1. We assume the patient accrual period of 36 months and the follow-up period of 12 months. The assumption that patients are randomized until the end of accrual. The sample size was estimated using SWOG ([https://www.swogstat.org/stat/public/one\\_survival.htm](https://www.swogstat.org/stat/public/one_survival.htm)) sample size calculator.

### *Cohort B (treated with one prior ALK inhibitor):*

A sample size of 15 patients achieves 80% power to detect the difference between the null hypothesis of median PFS of 7 months and the alternative hypothesis of median PFS of 14 months at two-sided significance level of 0.1. We assume the patient accrual period of 36 months and the follow-up period of 12 months. The assumption that patients are randomized until the end of accrual. The sample size was estimated using SWOG ([https://www.swogstat.org/stat/public/one\\_survival.htm](https://www.swogstat.org/stat/public/one_survival.htm)) sample size calculator.

## 9.3 Data Analyses Plans

We will use Kaplan-Meier methods to estimate the progression-free survival, time to 2nd and 3rd SABR and overall survival.

Duration of response (defined in 6.1.5) duration will be summarized for patients who responded. Descriptive summary statistics like median, 25% and 75% percentiles will be used.

Toxicities are dichotomized as none versus any, or none and mild versus moderate to severe.

The rates of overall response, toxicity and adverse events as well as their 95% confidence intervals will be estimated using exact binomial method.

We will compare the rates of toxicity and adverse events in this study with those of historical controls by the Fisher's exact test.

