**STUDY SUMMARY**

Title	Phase II trial of Ceritinib in combination with Stereotactic Ablative Radiation in ALK -rearranged metastatic lung adenocarcinoma
Short Title	Ceritinib and SABR in ALK + lung adenocarcinoma
Protocol Number	XXX
Phase	II
Methodology	Open label, Dual arm
Study Duration	Three years
Study Center(s)	single center
Objectives	Prolongation of progression free survival in lung adenocarcinoma with targeted therapy and radiation
Number of Subjects	33
Diagnosis and Main Inclusion Criteria	Metastatic/locally advanced lung adenocarcinoma harboring a ALK rearrangement
Study Product(s), Dose, Route, Regimen	Ceritinib (LDK378) 450 mg PO daily
Duration of administration	Until progression/intolerance of therapy. Projected 14 months for patients who progressed on crizotinib therapy and 20 months for those who have not been treated previously with an ALK inhibitor.
Reference therapy	Published progression free survival with ceritinib (LDK378) alone
Statistical Methodology	Sample size calculated on the basis of prolongation of progression free survival of patients treated on this protocol compared to published survival data. Kaplan Meier Methods will be used to estimate progression-free survival and overall survival

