### Cohort A (*ALK* inhibitor naive):

**Primary Objective:** To demonstrate the superiority of ceritinib combined with SABR in prolonging median PFS compared to historical control of 10 months

**Primary Endpoint:** Median PFS (as described in section 2.0) for study cohort, expected to be 20 months

**Hypothesis:** The addition of stereotactic radiation in patients with *ALK*+ lung adenocarcinoma receiving ceritinib will enhance efficacy leading to prolongation of time on ceritinib monotherapy.

**Secondary Objectives:** To describe overall survival in study participants  
To describe the time to 2nd and 3rd SABR therapy  
To determine the number of patients with CR, PR or stable disease by RECIST 1.1 criteria at 6 and 12 months

**Secondary Endpoints:** Overall survival  
Time to 2nd SABR treatment, Time to 3rd SABR treatment

PFS at 6 and 12 months from study initiation therapy

**Safety Objectives:** Demonstrate safety of ceritinib followed by SABR.

Safety Endpoints: toxicity and adverse events (CTCAE v.4)

**Hypothesis:** the safety of this combination of targeted therapy and radiation will be as safe as published experience of both these agents.

Cohort B (treated with one prior ALK-inhibitor):

**Primary Objective:** To demonstrate the superiority of ceritinib combined with SABR in prolonging median PFS compared to historical control of 7 months

Primary Endpoint: Median PFS (Time to subsequent systemic therapy) for study cohort, expected to be 14 months.

**Hypothesis:** the addition of stereotactic radiation in patients with ALK+ lung adenocarcinoma receiving ceritinib will enhance efficacy and prolongation of time on ceritinib monotherapy.

**Secondary Objectives:** To describe overall survival in study participants  
To describe the time to 2nd and 3rd SABR therapy  
To determine the number of patients with CR, PR or stable disease by RECIST 1.1 criteria at 6 and 12 months

Secondary Endpoints: Overall survival  
Time to 2nd SABR treatment, Time to 3rd SABR treatment  
PFS at 6 and 12 months from study initiation

**Hypothesis:** The combination of SABR and ceritinib will result in a clinically meaningful overall survival in study participants.

The early application of SABR will be effective in delaying progression which is amenable to SABR but does not require a change in systemic therapy

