### 2.3 Definition of end of the Study

The study will end when all 33 patients have evidence of disease progression by RECIST1.1, unacceptable toxicity, withdrawal of consent, or discontinuation of the trial for any other reason.

At the completion or discontinuation of study medication, all patients will be seen within 30 days for an end of therapy evaluation. This will include a safety assessment for AE's SAE's. Any unused medication will be returned.

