**Study Design:**

**Purpose:** of this prospective, single-center, two cohort, non-randomized trial is to evaluate the impact of the combination of ceritinib and stereotactic radiation delivered to patients with *ALK*-rearranged adenocarcinoma. The enhanced efficacy of this combination is to be evaluated specifically with regards to prolongation of clinical benefit of ceritinib. We will also evaluate the safety of this combination of targeted therapy and radiation.

For *ALK*-rearranged patients started on ceritinib and treated with SABR to persisting lesions:  
 -PFS compared to published historical results with ceritinib alone PFS=7 month for prior crizotinib treated and 10 month for no previous crizotinib therapy (Shaw et al, NEJM 2014).  
 PFS will be defined as Time to Subsequent Systemic Therapy.

As secondary objectives, we will also report overall survival and time to 2nd and 3rd SABR for each cohort.

	Objective	Endpoint
Primary:	Cohort A: Superiority of ceritinib + SABR median PFS compared to historical control of 10 months (expected to be 20 months)  Cohort B: Superiority of ceritinib + SABR median PFS compared to historical control of 7 months	Cohort A Median PFS defined as time from initiation of ceritinib until disease progression by RECIST 1.1, unacceptable toxicity, withdrawal of consent, or discontinuation of the trial for any other reason including death.  Cohort B: Median PFS defined as time from initiation of ceritinib until disease progression by RECIST 1.1, unacceptable toxicity, withdrawal of consent, or discontinuation of the trial for any other reason including death.
Secondary:	Report Overall survival  Report Time to 2 nd SABR  Report Time to 3 rd SABR  Report proportion of patients CR/PR/stable disease at 6 and 12 months	Overall survival  Time from start of systemic therapy to first day of second course of SABR  Time from start of therapy to first day of third course of SABR  Number of patients with CR/PR/stable disease for 6 and 12 months after initiation
Safety:	Demonstrate safety of ceritinib followed by SABR	Describe toxicity and adverse events (CTCAE v.4) compared to historical controls.

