### **9.4 Definition of end of the Study**

Cohort A will be completed when 20 patients and cohort B will be completed when 17 patients have evidence of disease progression by RECIST not amenable to SABR requiring discontinuation of ceritinib, unacceptable toxicity, withdrawal of consent, or discontinuation of the trial for any other reason.

At the completion or discontinuation of study medication, all patients will be seen within 30 days for an end of therapy evaluation. This will include a safety assessment for AE's SAE's. Any unused medication will be returned.

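### Superiority of median PFS over 10 and 7 months is claimed and powered, but no PFS test, confidence level or success rule is planned, so the stated 80% power and alpha of 0.1 attach to no analysis

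*Combined protocol and SAP*

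**What the plan says.** **Objective.** Section 2.0 sets the Cohort A primary objective as "To demonstrate the superiority of ceritinib combined with SABR in prolonging median PFS compared to historical control of 10 months", and the Cohort B objective is worded the same way against 7 months. The table in Section 9.1 repeats both, for B as "Superiority of ceritinib + SABR median PFS compared to historical control of 7 months". The hypothesis text at the end of Section 2.0 is weaker: there the primary objective is to describe PFS.

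**Sizing.** Section 9.2 states for A "A sample size of 18 patients achieves 80% power to detect the difference between the null hypothesis of median PFS of 10 months" against 20 months, and for B "A sample size of 15 patients achieves 80% power to detect the difference between the null hypothesis of median PFS of 7 months" against 14 months. Both use a two-sided level of 0.1, 36 months of accrual and 12 months of follow-up. Both cite an online one-sample survival calculator.

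**Analysis.** Section 9.3: "We will use Kaplan-Meier methods to estimate the progression-free survival". The Study Summary agrees: "Kaplan Meier Methods will be used to estimate progression-free survival and overall survival". The 95% intervals in Section 9.3 are for response, toxicity and adverse-event rates, and its one test, Fisher's exact, is for toxicity and adverse events. Section 9.7, on statistical methods, is a heading without text. Section 9.10.1 excludes imputation but gives no censoring rule.

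**Related inputs.** Section 2.3: "The study will end when all 33 patients have evidence of disease progression by RECIST1.1" or have stopped for another listed reason. Section 9.4: "Cohort A will be completed when 20 patients and cohort B will be completed when 17 patients" have reached a similar list of endpoints. The Full Analysis Set is assigned to baseline data and the Safety Set to treatment and safety. Neither is assigned to PFS.

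**The concern.** A null, an alternative, an alpha and a power describe a hypothesis test. The analysis section does not contain one. Estimating a Kaplan-Meier curve does not by itself show that a median exceeds 10 or 7 months; that needs a statistic and a threshold fixed beforehand.

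This matters more than usual here. The trial is open-label and non-randomised, and each small cohort is judged against a fixed historical number. A pre-specified rule is then the main protection against picking the favourable analysis once the data are known. With 18 and 15 patients, reasonable rules can give opposite answers on the same data.

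**Working it through.** **Inputs (Section 9.2).** A: N = 18, medians 10 vs 20 months. B: N = 15, medians 7 vs 14. Two-sided alpha 0.1, so 0.05 in the superiority direction. Accrual 36 months, follow-up 12. *Assumed:* exponential PFS, uniform accrual, no dropout.

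**Step 1. Reproduce the plan's sample sizes.** With hazard λ = ln 2 / median, the probability of an event by month 48 is p = 1 − [exp(−12λ) − exp(−48λ)] / (36λ).

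| | p under null | p under alternative |
|---|---|---|
| A | 0.840 | 0.623 |
| B | 0.917 | 0.742 |

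For a one-sample test on the log hazard, N = [(1.645/√p0 + 0.842/√p1) / ln 2]².
- A: [(1.795 + 1.066)/0.693]² = 17.04, that is 18.
- B: [(1.718 + 0.977)/0.693]² = 15.11, that is 16, against 15 stated.
- Power at the stated N: 81.7% and 79.8%.

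Two-sided 0.05 would give 21.4 and 19.0, which does not match. The calculator's formula is not in the documents, so the method is inferred from this match.

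**Step 2. A test that fits the sizing.** One-sample log-rank: O is the number of PFS events, E is total follow-up × ln 2 / null median, and success means Z > 1.645. Simulation of 400,000 trials per cohort and hypothesis, cutoff at month 48:

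| Variance | A: error / power | B: error / power |
|---|---|---|
| (E+O)/2 | 0.051 / 0.824 | 0.050 / 0.806 |
| E | 0.036 / 0.781 | 0.035 / 0.764 |

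An exponential maximum-likelihood test has about 78% and 76% power. Error here is the upper-tail error under the null.

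**Step 3. Illustration: rules based on Kaplan-Meier.** The plan states none of these. Everyone has at least 12 months of potential follow-up, so no one is censored before 10 or 7 months. The Kaplan-Meier estimate at the null median is then a simple proportion, with true value 0.5 under the null and 2^(−0.5) = 0.707 under a doubled median.

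*90% lower limit above the null median.* For the plain limit in A, 13/18 gives 0.722 − 1.645 × 0.106 = 0.549, which passes; 12/18 gives 0.667 − 1.645 × 0.111 = 0.484, which fails. The other thresholds follow in the same way.

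| Rule | Needs | Error | Power |
|---|---|---|---|
| A plain or log-log | ≥13 of 18 | 0.048 | 0.561 |
| A log | ≥12 of 18 | 0.119 | 0.744 |
| B plain or log | ≥11 of 15 | 0.059 | 0.540 |
| B log-log | ≥12 of 15 | 0.018 | 0.318 |

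*Kaplan-Meier median simply above the null.* Error is P(≥10 of 18) = 0.41 in A and P(≥8 of 15) = 0.50 in B.

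**Step 4. Choosing after the fact.** Under the null, claiming success if either the log-rank test or the 90% plain limit succeeds has upper-tail error of about 8% (A) and 9% (B).

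**Step 5. The cutoff matters.** Log-rank power with variance (E+O)/2 and a true doubling:

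| Cutoff | A | B |
|---|---|---|
| Month 48 | 82% | 81% |
| 12 months after last enrolment, 36-month accrual | 81.3% | 79.5% |
| 12 months after last enrolment, 24-month accrual | 78.5% | 77.7% |
| All followed to an event | 90% | 85% |

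**The case against.** **The plan uses Kaplan-Meier to estimate, not to decide.** This stands. A reader might infer that the planned Kaplan-Meier analysis has only 56% or 32% power. The documents do not support that: no rule based on a Kaplan-Meier limit appears in them, and estimation alone has no power at all. The Step 3 figures only show how much the answer depends on an unstated rule. They also vary with the type of limit.

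**Section 9.2 already points to a one-sample survival test.** Largely true: null, alternative, alpha, accrual, follow-up and a one-sample calculator are all given. But they are given for sample size only, and Section 9.3 adopts no matching test. Step 2 shows that even close relatives differ, from 76% to 82% power. A reader might also infer that the cohorts are too small. They are not: 18 and 15 fit the stated design.

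**The 8% and 9% errors need an analyst who tries two rules and keeps the better.** Correct. They are conditional, and nothing in the documents suggests such an intention.

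**Sections 2.3 and 9.4 define the end of the study, not a data cutoff.** Fair. The 36 + 12 months in Section 9.2 are the nearest thing to a cutoff, and the differing patient counts are a separate inconsistency. The analysis set is also a small matter: Section 5.2.3.3 lets patients who never received drug be replaced, and PFS starts at first ceritinib, so enrolled and treated patients should differ little.

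**Conclusion.** The point holds and should be corrected before analysis. The protocol claims superiority and states power and alpha, but plans no analysis to which they apply. Followed as written, it yields two Kaplan-Meier curves and no basis for declaring superiority.

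The sample sizes are not at fault. With a one-sample log-rank test the design delivers roughly what it promises: about 82% and 81% power with variance (E+O)/2 and a month-48 cutoff, or about 76–78% with variance E or an exponential test. That the text names no test or rule comes from reading it and depends on no model. The sizes of the consequences rest on the assumptions listed above.

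**What to change.** **Add to Section 9.3, for each cohort:**
- **Test.** PFS in all patients who received ceritinib is tested against an exponential distribution with median 10 (A) or 7 (B) months by a one-sample log-rank test, Z = (E − O)/√((E + O)/2), at two-sided alpha 0.1. Superiority is declared if Z > 1.645.
- **Cutoff.** Choose one: 48 months after the cohort opens, or 12 months after its last enrolment. With the second, restate power as about 81% and 79–80% for 36-month accrual.
- **Censoring.** For example, patients event-free at the cutoff are censored at their last evaluable tumour assessment.
- **Estimate.** Report O/E, the hazard ratio against the null, with a 90% interval. Inverting the same statistic gives limits (O + c²/4 ± c√(O + c²/16))/E with c = 1.645, so the upper limit is below 1 exactly when Z > 1.645.
- **Kaplan-Meier.** Report the median and its interval as descriptive only, noting that the interval may include the null median when the test is positive. In B, under a true doubling, about 61% of log-rank successes would sit beside a 90% log-log lower limit that does not exceed 7 months.

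**Reconcile elsewhere:**
- Use one PFS event definition in Sections 2.0, 6.1.6 and 9.1. They now differ on whether progression treated with further SABR counts, and on whether PFS means time to subsequent systemic therapy. The test needs this, because O depends on it.
- Align the descriptive wording of the objective in Section 2.0 with the superiority objective.
- Reconcile the counts: 33 in Section 2.3 against 20 + 17 = 37 in Section 9.4.

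If only description is intended, remove superiority from Sections 2.0 and 9.1 and the power claim from Section 9.2.

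**Cost.** One paragraph and a few aligned sentences, with no extra patients or data. The event definition takes more thought, since the sponsor must decide which reading is meant.

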#### Subsequent areas of progression:

As long as the study participant is on ceritinib as the sole systemic therapy, further stereotactic radiation may be delivered to up to 6 sites or organs at a time. When ceritinib is no longer the systemic agent or when new progressive sites cannot feasibly be treated with stereotactic radiation (e.g., malignant pleural effusion or site previously irradiated), study participation will end. The primary endpoint of progression-free survival will be calculated from the start of treatment to the first episode of progression.

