#### 4.1.2 Treatment duration

Patients will continue ceritinib treatment until they experience any of the following:

- Disease progression not amenable to SABR and necessitating change in systemic therapy determined by the treating physician.
- Unacceptable toxicity that precludes further treatment.
- Start of a new anti-cancer therapy.
- Pregnancy.
- Treatment is discontinued at the discretion of the investigator or patient.
- Lost to follow-up.
- Death.
- Completed.

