#### **5.2.3.2 Criteria for patient withdrawal**

Patients may voluntarily withdraw from the study (no further study data to be collected) at any time.

Patient death will be considered as a withdrawal from the study. Patients may also be withdrawn (the physician may decide to remove the patient from any further study activity) if any of the following occur:

- Adverse event(s) (see [Section 7.1](#))
- Disease progression
- Major protocol deviation
- Technical problems
- Physician decision

- Non-compliance with study treatment.
- Death
- Completed

Patients must be withdrawn if any of the following occur:

- Lost to follow-up
- Subject/guardian decision
- Pregnancy (Pregnancy will be followed for outcome)

Patients lost to follow up should be recorded as such in the clinical trial record. For patients who are lost to follow-up, the investigator will record the attempts at “due diligence” by documenting in the source documents steps taken to contact the patient, e.g. dates of telephone calls, registered letters, etc.

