### 6.1.6 Progression-Free Survival

Progression Free Survival will be the primary endpoint for this study. If oligoprogression occurs that is amenable to repeat treatment with SABR, the ceritinib will be held and SABR therapy delivered. If the treating oncologist then feels the patient would benefit from continuing the ceritinib that will be permitted. The patient will however be deemed as having progressed even if ceritinib is resumed.

After the initial SABR to persisting lesions if new lesions appear or if existing lesions enlarge but are NOT amenable to SABR (necessitating a change in systemic therapy), the patient will have completed the therapeutic portion of the study.

Time to 2nd SABR is defined as the duration of time from the start of treatment to the time of development of new or enlarging lesions that are amenable to SABR and the progression does not require a discontinuation of ceritinib.

Time to 3rd SABR is defined in patients who have already received two rounds of SABR while on this study as the duration of time from the start of treatment to the time of development of new or enlarging lesions that are amenable to SABR and the progression does not require a discontinuation of ceritinib.

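### Time to 2nd and 3rd SABR is to be estimated by Kaplan-Meier with no rule for outcomes that rule out further SABR; with usual censoring, the probability of repeat SABR is overstated and the median time is too short

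*Combined protocol and SAP*

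**What the plan says.** Section 9.3 names one estimator for four endpoints. It begins "We will use Kaplan-Meier methods to estimate the progression-free survival" and goes on to list time to 2nd and 3rd SABR and overall survival. Describing the time to 2nd and 3rd SABR is a secondary objective in both cohorts (Section 2.0 and the table in Section 9.1).

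The event is defined in two ways. Section 6.1.6 uses the development of "new or enlarging lesions that are amenable to SABR and the progression does not require a discontinuation of ceritinib". The table in Section 9.1 uses "Time from start of systemic therapy to first day of second course of SABR". For the 3rd course, Section 6.1.6 defines the endpoint "in patients who have already received two rounds of SABR while on this study", but still counts time from the start of treatment.

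Several outcomes close the way to a further SABR course on study:

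- **Progression that SABR cannot treat.** Section 4.1.2 lists "Disease progression not amenable to SABR and necessitating change in systemic therapy determined by the treating physician" as a reason to stop ceritinib. Section 6.1.6 says of such a patient that "the patient will have completed the therapeutic portion of the study".
- **Ceritinib stopped, or SABR not feasible.** Section 1.3.3 (Subsequent areas of progression) ends participation "When ceritinib is no longer the systemic agent or when new progressive sites cannot feasibly be treated with stereotactic radiation".
- **Death.** Section 5.2.3.2 states: "Patient death will be considered as a withdrawal from the study".

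Section 9.10.1 has censoring in its heading but deals only with missing data. No section gives a censoring rule, a cumulative incidence function or any other competing-risk method for these endpoints.

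**The concern.** Kaplan-Meier treats a censored patient as someone who could still have the event, with the same future chance as those still under observation. That suits a patient whose follow-up has simply ended. It does not suit a patient who has died, changed systemic therapy or left the therapeutic part of the trial, because by the protocol's own rules that patient cannot have another study SABR.

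If these patients are censored, one minus Kaplan-Meier describes repeat SABR in a hypothetical setting where systemic failure never happens. The trial's concept is that limited progression can be treated with repeat SABR while ceritinib continues (Sections 1.1.5 and 1.4). How often and how soon that happens would look more favourable than it is, most of all where systemic failure is common.

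**Working it through.** The plan states no figure for time to 2nd or 3rd SABR, so there is none to reproduce. The check shows the direction and likely size of the error for the 2nd course.

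**Inputs**

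- Median PFS under the design alternative: 20 months (cohort A) and 14 months (cohort B). Historical medians: 10 and 7 months (Section 9.2).
- Accrual of 36 months and follow-up of 12 months (Section 9.2).
- Share *s* of first failures that are amenable to SABR: not in the documents. Assumed 25% to 75%. One point, 64%, is borrowed from Section 1.1.4, where it is the share progressing at known sites; that is not the same quantity.
- Constant hazards, with PFS ended by the first failure of either kind, as Section 6.1.6 has it.

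**Formulas**

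- Total hazard *h* = ln 2 / median PFS.
- One minus Kaplan-Meier, precluding events censored: 1 − exp(−*s h t*).
- Actual probability of a 2nd SABR (cumulative incidence): *s* × [1 − exp(−*h t*)].

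**Worked case, 50% share, 24 months**

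- Cohort A: *h* = 0.6931/20 = 0.03466. One minus Kaplan-Meier = 1 − exp(−0.4159) = 34.0%. Incidence = 0.5 × [1 − exp(−0.8318)] = 28.2%.
- Cohort B: *h* = 0.6931/14 = 0.04951. One minus Kaplan-Meier = 1 − exp(−0.5941) = 44.8%. Incidence = 0.5 × [1 − exp(−1.1882)] = 34.8%.

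**24-month results**

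| Cohort and median PFS | Share | 1 − KM | Incidence | Excess (points) |
|---|---|---|---|---|
| A, 20 months | 25% | 18.8% | 14.1% | 4.7 |
| A, 20 months | 50% | 34.0% | 28.2% | 5.8 |
| A, 20 months | 64% | 41.3% | 36.1% | 5.2 |
| A, 20 months | 75% | 46.4% | 42.4% | 4.0 |
| B, 14 months | 25% | 25.7% | 17.4% | 8.3 |
| B, 14 months | 50% | 44.8% | 34.8% | 10.0 |
| B, 14 months | 64% | 53.3% | 44.5% | 8.8 |
| B, 14 months | 75% | 59.0% | 52.1% | 6.9 |
| A, 10 months (historical) | 50% | 56.5% | 40.5% | 16.0 |
| B, 7 months (historical) | 50% | 69.5% | 45.4% | 24.1 |

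At 12 months, with a 50% share and the design alternatives, the gap is small: 18.8% against 17.0% in A and 25.7% against 22.4% in B.

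**Simulation.** With 4,000 trials per setting, 18 and 15 patients, and follow-up spread over 12 to 48 months, the 50% share gave a mean one minus Kaplan-Meier of 33.9% (A) and 44.6% (B). Aalen-Johansen gave 28.1% and 34.5%, against 28.2% and 34.8% in the model.

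**Median times at the design alternatives.** At a 64% share, the Kaplan-Meier median is 20/0.64 = 31.3 months in A and 14/0.64 = 21.9 in B. The times at which incidence reaches 50% are −ln(1 − 0.5/0.64)/*h* = 43.9 and 30.7 months. At a 50% share, Kaplan-Meier gives 40 and 28 months, although incidence never passes 50%.

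**Direction.** 1 − exp(−*s h t*) is concave in *s*, is zero at *s* = 0 and equals the incidence formula at *s* = 1. It therefore exceeds the incidence for every share strictly between 0 and 1.

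**Counting precluding outcomes as events.** This does not help. The 24-month figures become 1 − exp(−*h t*) = 56.5% (A) and 69.5% (B), which describe any failure and not SABR.

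**The case against.** The strongest reply is that the censoring is inferred. A reader might take it that the plan instructs the analyst to censor these patients, but no section says so. If they were kept in the risk set as event-free, the bias would vanish. That is correct, and it is why the conclusion is conditional. The plan does not say that either, however, and censoring is the standard use of the method it names.

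A reader might also infer that the proportion of patients salvaged by repeat SABR is a stated secondary objective. It is not. Section 2.0 asks only for a description of the time to 2nd and 3rd SABR, and no section plans a 24-month probability. The point still stands for the planned endpoint, since a Kaplan-Meier curve and its median carry the same distortion.

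The size is also open to challenge. The amenable share is assumed, and the model lets a 2nd SABR occur from day 1 although the first follows at least 10 weeks of ceritinib (Sections 1.4 and 2.2.1). The excess is also within sampling error: binomial standard errors are √(0.282 × 0.718/18) = 10.6 points in A and √(0.348 × 0.652/15) = 12.3 in B, against gaps of 5.8 and 10.0. All of this stands and limits the weight of the point. It does not make an avoidable systematic error acceptable.

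**Conclusion.** The concern holds in conditional form. Kaplan-Meier is named for two endpoints whose event can be ruled out by death, progression not amenable to SABR or permanent ceritinib discontinuation, and nothing says how those outcomes are handled. With usual censoring, the probability of repeat SABR is overstated by about 4 to 6 points in cohort A and 7 to 10 in cohort B at 24 months under the design alternatives, and by more if PFS stays at the historical medians. These sizes rest on constant hazards and a share of 25% to 75%. The direction does not depend on the share.

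Because the endpoints are times, a reader might infer that the reported times would be too long. The reverse is true: the probability is too high and the median too short. Nor does the point reach the primary analysis: Kaplan-Meier remains suitable for PFS and overall survival, and no test is planned on these two endpoints.

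No size is offered for the 3rd course. Its difficulty comes earlier: patients enter the defined group only after two rounds, so the time before that is necessarily free of the event, yet it is counted.

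**What to change.** In Section 9.3, keep Kaplan-Meier for PFS and overall survival. For time to 2nd and 3rd SABR:

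- Estimate Aalen-Johansen cumulative incidence from the first ceritinib dose, with 12- and 24-month values and 95% confidence intervals.
- Treat as competing events death, progression not amenable to SABR, and permanent ceritinib discontinuation other than through loss to follow-up. The exception matters because Section 4.1.2 lists loss to follow-up among the reasons ceritinib stops.
- Censor loss to follow-up and administrative end of follow-up, and state this in Section 9.10.1.
- Use one event definition: reconcile Section 6.1.6 (amenable lesions appear) with the Section 9.1 table (first day of the SABR course).
- State the denominator for the 3rd course: either all treated patients from first dose or, if limited to patients with two rounds, time from the 2nd course.

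The cost is a short rewrite of Sections 9.3 and 9.10.1 and alignment of two definitions. The routine is standard, and the date and reason for stopping ceritinib and survival status are already collected (Sections 5.2.3.1 and 5.1.16). The sample size, visits and treatment rules do not change. The reported figures would be less favourable.
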